- c. During the weekly follow-up visits, only ongoing AEs and new AEs assessed by the investigator to be related to study drug will be recorded and the concomitant medications associated with these AEs.

- d. In addition, during the weekly follow-up visits, AEs of urinary tract infection (UTI), hospital-acquired/ventilator-associated pneumonia, myocardial infarction (MI), sepsis from any source, critical illness myopathy/neuropathy, significant hypotension requiring support of vasopressors will be recorded regardless of relatedness. Associated concomitant medications for these AEs will not be recorded.
- e. All SAEs regardless of relationship to study drug and their associated concomitant medications will be recorded from the time of study drug initiation through the last follow-up visit/contact.
- f. For subjects who early terminate from the study, prior to discontinuation as much information as is available should be recorded for ongoing AEs/SAEs, new AEs/SAEs and their associated concomitant medications, especially those that may have led to the early termination.

For some of the concomitant medications only the highest dose administered will be required in the eCRF. Reference the eCRF Completion Guidelines for guidance.

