u. AEs and concomitant medications will be collected throughout the study; non-direct questioning will occur. The collection requirements will differ depending on the subject's treatment progression as follows: 1. All adverse events and associated concomitant medications will be collected through the in-patient follow-up day. 2. IV anesthetic agents (midazolam, propofol, thiopental, pentobarbital, or ketamine) administered during the study drug treatment period and the in-patient follow-up day should be followed through the week 4 visit/contact. 3. During the weekly follow-up visits, only ongoing AEs and new AEs assessed by the investigator to be related to study drug will be recorded and the concomitant medications associated with these AEs. 4. In addition, during the weekly follow-up visits, AEs of urinary tract infection (UTI), hospital-acquired/ventilator-associated pneumonia, myocardial infarction (MI), sepsis from any source, critical illness myopathy/neuropathy, significant hypotension requiring support of vasopressors will be recorded regardless of relatedness. Associated concomitant medications for these AEs will not be recorded. 5. All SAEs regardless of relationship to study drug and their associated concomitant medications will be recorded from the time of 1st dose through the last follow-up visit/contact. 6. For subjects who early terminate from the study, prior to discontinuation as much information as is available should be recorded for ongoing AEs/SAEs, new AEs/SAEs and their associated concomitant medications, especially those that may have led to the early termination.

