Potential subjects must have failed one 2nd line IV AED therapy, administered at an appropriate dose and duration to show efficacy. Ganaxolone IV solution (open-label group) or ganaxolone IV solution or placebo (double-blind group) will be administered in combination with standard of care at the time that the first 2nd line IV AED has failed and the second 2nd line AED is medically indicated during the treatment of SE. Study drug must be administered with 2nd line IV AED treatment and should be initiated as close to the dose initiation of the second 2nd line IV AED as possible.

Upon administration of study drug, subjects will be monitored for improvement or resolution of SE (clinical or EEG response).

Note, the infusion rate cannot be rounded-up regardless whether dosing is in subjects  $\geq 40$  kg or  $< 40$  kg.

Subjects weighing at least 40 kg:

- A 30-mg bolus dose (over ~3 minutes) will be administered with a continuous infusion of 80 mg/hour for 2 hours followed by a continuous infusion rate of 40 mg/hour for 10 hours, and then 20 mg/hour for the remaining 12 hours of Day 1.
- On Day 2 (24-36 hours) the continuous infusion rate of 20 mg/hour will continue until the start of the study drug taper at 36 hours post study drug initiation. If needed, to manage seizure relapse or another medical reason, the infusion rate can be increased from 20 mg/hour up to a maximum rate of 45 mg/hour at any time during hours 24-36 of Day 2.
- To taper the study drug, the infusion rate at the 36-hour post study drug initiation timepoint will be reduced by 33.3% every 4 hours until the infusion is stopped or if the infusion rate becomes too low to sustain the infusion line, at which point it will be stopped. The first taper will be 33.3% from the current infusion rate, the second taper will be 33.3% from the first tapered infusion rate, and the final taper will be 33.3% from the previous tapered infusion rate. If, per the investigator's judgment, the study drug taper needs to start at an earlier timepoint during the treatment period, the infusion rate at the start of the first taper will be decreased by 33.3% every 4 hours as described.
- At the time the study drug infusion is discontinued the subject will progress to the in-patient follow-up day assessments/procedures.

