#### **7.2.3.3 Adverse Event Collection**

Subjects and their parent/guardian/LAR will be questioned in a general way to ascertain if AEs have occurred (e.g., "Have you had any health problems since your last visit?"). Adverse events are collected from the time of first dose of study drug through the last follow-up visit/contact.

Refer to Section 8, Adverse and Serious Adverse Events Assessment.

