## 8. ADVERSE AND SERIOUS ADVERSE EVENTS ASSESSMENT

### 8.1 Definition of Adverse Events, Period of Observation, Recording of Adverse Events

An AE is any untoward medical occurrence in a clinical investigation subject who has been administered a pharmaceutical product; it does not necessarily have a causal relationship with this treatment. An AE can therefore be any unfavorable and unintended sign (including an abnormal laboratory finding), symptom, or disease temporally associated with the use of a medicinal (investigational) product, whether or not related to the medicinal (investigational) product.

As this study allows for pre-consenting of subjects, all AEs will be collected from the time of first dose of study drug until the defined follow-up period stated in Section 7.1.3. Where possible, a diagnosis rather than a list of symptoms should be recorded. If a diagnosis has not been made, then each symptom should be listed individually. All AEs should be recorded on the appropriate AE pages in the eCRF and in source documents. In addition to untoward AEs, unexpected benefits outside the study drug indication should also be recorded on the AE eCRF page.

All AEs must be followed for the durations described below. For AEs followed to closure, this indicates that an outcome is reached, stabilization is achieved (the investigator does not expect any further improvement or worsening of the event), or the event is otherwise explained. When appropriate, medical tests and examinations are performed so that resolution of event(s) can be documented.

For subjects who:

- a. Have 2 days of treatment which includes a 12-hour study drug taper, all adverse events will be collected through the in-patient follow-up day. During the weekly follow-up visits only, ongoing AEs and new AEs assessed by the investigator to be related to study drug will be recorded. All SAEs regardless of relationship to study drug will be recorded from the time of 1st dose through the last follow-up visit/contact.

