- b. Stop study drug administration without a study drug taper but continue with the follow-up visits, all adverse events will be collected through the in-patient follow-up day. During the weekly follow-up visits, only ongoing AEs and new AEs assessed by the investigator to be related to study drug will be recorded. All SAEs regardless of relationship to study drug will be recorded from the time of 1st dose through the last follow-up visit/contact. Additionally, AEs of UTI, hospital-acquired/ventilator-associated pneumonia, MI, sepsis from any source, critical illness myopathy/neuropathy and significant hypotension requiring vasopressor support will be recorded as AEs regardless of relatedness.
- c. Early terminate from the study, prior to discontinuation as much information as is available should be recorded on any on-going AEs/SAEs and AEs/SAEs that may have led to the early termination.

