### **8.2.3 Serious Adverse Event Definition**

An SAE is any untoward medical occurrence (whether considered to be related to study drug or not) that at any dose:

- Results in death
- Is life-threatening. Note: The term "life-threatening" in the definition of "serious" refers to an event in which the subject was at risk of death at the time of the event; it does not refer to an event that hypothetically might have caused death if it were more severe.
- Requires in-patient hospitalization or prolongation of existing hospitalization. Note: Hospitalizations, which are the result of elective or previously scheduled surgery for preexisting conditions that have not worsened after initiation of treatment, should not be classified as SAEs. For example, an admission for a previously scheduled ventral hernia repair would not be classified as an SAE; however, a complication resulting from a

hospitalization for an elective or previously scheduled surgery that meets serious criteria must be reported as an SAE.

- Results in persistent or significant disability or incapacity
- Is a congenital abnormality or birth defect
- Is an important medical event. Note: Important medical events that may not result in death, be life-threatening, or require hospitalization may be considered an SAEs when, based on appropriate medical judgment, they jeopardize the patient and may require medical or surgical intervention to prevent one of the outcomes listed in this definition. Examples of such medical events include allergic bronchospasm requiring intensive treatment in an emergency room or at home; blood dyscrasias or convulsions that do not result in in-patient hospitalization; or the development of drug dependency or drug abuse.

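### Protocol Section 8.1 item a (tapered subjects) omits the rule to record six named AE types at the weekly visits that the synopsis and Table 1 apply to all subjects

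*Protocol*

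**What the plan says.** Section 8.1 of the protocol sets AE recording by how the subject leaves treatment.

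- **Item a** covers subjects with 2 days of treatment including the 12-hour taper. For the weekly visits it says: "During the weekly follow-up visits only, ongoing AEs and new AEs assessed by the investigator to be related to study drug will be recorded". It then adds the SAE rule, "All SAEs regardless of relationship to study drug will be recorded from the time of" first dose to the last contact, and ends there.
- **Item b** covers subjects who stop without a taper and stay in follow-up. It has the same base rule and the same SAE rule, then one more sentence: "Additionally, AEs of UTI, hospital-acquired/ventilator-associated pneumonia, MI, sepsis from any source, critical illness myopathy/neuropathy and significant hypotension requiring vasopressor support will be recorded as AEs". That sentence applies whether or not the investigator judges the event related.

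Two other places give the named-event rule with no mention of taper. Synopsis item 17d reads: "In addition, during the weekly follow-up visits, AEs of urinary tract infection (UTI), hospital-acquired/ventilator-associated pneumonia, myocardial infarction (MI), sepsis from any source", and continues through the same list. Table 1 footnote u(4) ends its identical list with "significant hypotension requiring support of vasopressors will be recorded regardless of relatedness". Both add that concomitant medications linked to these events are not recorded.

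On a related matter, Section 5.2 follows IV anesthetics to the last contact only in no-taper subjects, and only if the agent was started on the in-patient follow-up day. Synopsis 17b and Table 1 footnote u(2) also include agents given during the treatment period, with no taper condition.

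**The concern.** For one and the same event in a tapered subject, footnote u(4) says record it and item a gives no ground for recording it. Two sites could each follow the protocol and return different data.

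The split also runs along an outcome. Under Sections 5.2.2 and 6.2.3, a subject who progresses to an IV anesthetic for seizure suppression stops study drug without a taper. Under Section 8.1 as written, such subjects have the named complications recorded at Weeks 2 to 4 whatever the cause, while subjects who complete the taper do not. A comparison of late infections or cardiovascular events by taper status, or between groups with different shares of tapered subjects, would partly reflect the recording rule.

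SAP Section 4.9.1 counts AEs with onset up to the end of follow-up as treatment-emergent, so events at Weeks 2 to 4 belong in the AE tables if they are recorded.

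**Working it through.** No figure applies; the check is a comparison of the current passages.

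**Step 1. Where the named-event rule appears.**

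| Place | Subjects covered | Named events recorded regardless of relatedness | Limited to weekly visits | Concomitant medications exempted |
|---|---|---|---|---|
| Synopsis 17d | no taper condition | yes | yes | yes |
| Table 1 footnote u(4) | no taper condition | yes | yes | yes |
| Section 8.1 item b | no taper, continuing | yes | not stated in that sentence | not stated |
| Section 8.1 item a | 2 days including taper | absent | – | – |

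**Step 2. Which events are affected in a tapered subject at Weeks 2 to 4.**

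- Any SAE: recorded under every version.
- An AE already ongoing: recorded under every version.
- A new, non-serious AE judged related: recorded under every version.
- A new, non-serious, unrelated AE that is not on the list: outside the weekly recording rules in all four places.
- A new, non-serious, unrelated AE on the list: recorded under 17d and u(4), not provided for in item a.

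Only the last class is in dispute. It shrinks further because several listed events would often be serious; Section 8.2.3 includes "Requires in-patient hospitalization or prolongation of existing hospitalization" among its criteria. It is not empty. The guidance in Section 8.1.2 treats an event readily explained by the underlying condition or other therapy as not related, and a non-serious UTI in a hospitalized subject could well be judged that way.

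**Step 3. Subjects in neither item.** Section 6.2.3 provides for the case where "the study drug taper needs to start at an earlier timepoint during the treatment period". Such a subject does not have the 2 days of treatment named in item a and has not stopped without a taper as in item b. Only the synopsis and Table 1 clearly cover this subject.

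**Step 4. IV anesthetics in Section 5.2.** For no-taper subjects the difference is narrow. An anesthetic for seizure suppression stops study drug (Section 5.2.2), and the in-patient follow-up day begins at that moment (Section 3.1), so the two start windows almost meet. The clearest uncovered case is a tapered subject who starts an anesthetic on the in-patient day: 17b and u(2) follow the agent to Week 4, and this bullet of Section 5.2 does not. The start would still be captured, because Section 5.2 collects all concomitant medications through that day. What can be lost is the later course, unless the agent is tied to an SAE or to an ongoing or related AE.

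**The case against.** The strongest reply is that intent is clear and a site is unlikely to rely on item a alone. Section 7.2.3.3 says "Adverse events are collected from the time of first dose of study drug through the last follow-up visit/contact", and the opening of Section 8.1 is to the same effect. Section 7.1.3 has sites follow up SAEs and non-serious AEs at these contacts and points to Table 1 for what to collect. Item a's comma also falls after the word only, so read literally it is silent on the named events and does not forbid them.

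Part of this stands. Item a reads as a drafting omission, and the balance of the text favors recording. It does not settle the matter. The general sentences are narrowed for the weekly visits by synopsis 17c, footnote u(3) and item a, and Section 7.1.3 refers to both Section 8.1 and Table 1 without ranking them. The presence of the sentence in item b invites the reading that its absence from item a is meant.

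Three stronger readings are tempting, and the documents do not support them:

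- **That serious complications are lost in tapered subjects.** The SAE rule is the same in both items.
- **That the protocol deliberately chose lighter recording after a taper.** No passage gives a reason for it, and the synopsis and Table 1 say otherwise.
- **That the SAP's AE tables are distorted.** The SAP is written to Amendment 3, its schedule has an 18-hour taper, and its footnote v has no named-event rule for any subject. Nothing shows that an analyzed subject was followed under Amendment 4, although nothing excludes it.

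**Conclusion.** A real internal inconsistency, of minor weight. Three places carry the named-event rule, one of them for no-taper subjects only, and Section 8.1 item a does not carry it. The effect is confined to new, non-serious, unrelated named AEs in tapered subjects at Weeks 2 to 4, with early-taper subjects left uncertain under Section 8.1.

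The number of events cannot be estimated: the documents give no event rate, no share of tapered subjects and no count of subjects followed under the current text. The effect on the analyzed data may be nil. The SAP summarizes open-label data descriptively, so no inferential test is affected, and the primary endpoint concerns the first 24 hours.

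The conclusion rests only on the current wording and on no assumption about rates. The Section 5.2 mismatch is separate and narrower.

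**What to change.** 1. **Section 8.1.** Replace the split wording on named events in items a and b with the rule in synopsis 17d and footnote u(4), applied to all subjects who continue to the weekly visits, whatever the status or timing of their taper. Keep both the limit to the weekly visits and the statement that associated concomitant medications are not recorded. Copying item b's sentence into item a would not be enough, because that sentence contains neither element.
2. **Section 5.2.** Reconcile the IV-anesthetic bullet with synopsis 17b and footnote u(2) on both population and start window, so that a tapered subject who starts an agent on the in-patient day is handled the same way in all three places.
3. **SAP Section 4.9.1.** Only if an analyzed subject was followed under Amendment 4, note at the treatment-emergent AE tables that recording of these events at Weeks 2 to 4 may differ by taper status or protocol version.

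The drafting is a few sentences, almost all of it wording the protocol already contains. A protocol change still needs sponsor and IRB/EC approval (Section 10.3.2), so it is best carried in an amendment made for other reasons. It cannot change how data already collected were recorded.

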#### 8.1.1 Severity Categorization

The severity of AEs must be recorded during the course of the event, including the start and stop dates for each change in severity. An event that changes in severity should be recorded as a new

event. Worsening of pretreatment events, after initiation of the study drug, must be recorded as new AEs on the appropriate eCRF page.

The medical assessment of severity is determined by using the following definitions:

**Mild:** A type of AE that is usually transient and may require only minimal treatment or therapeutic intervention. The event does not generally interfere with usual activities of daily living.

**Moderate:** A type of AE that is usually alleviated with specific therapeutic intervention. The event interferes with usual activities of daily living, causing discomfort, but poses no significant or permanent risk of harm to the research subject.

**Severe:** A type of AE that interrupts usual activities of daily living, that significantly affects clinical status, or that may require intensive therapeutic intervention.

### 8.1.2 Relationship Categorization

A physician/investigator must make the assessment of relationship between the study drug and each AE. The investigator should decide whether, in their medical judgment, there is a reasonable possibility that the event may have been caused by the study drug. If there is no valid reason for suggesting a relationship, the AE should be classified as “not related.” Otherwise, if there is any valid reason, even if undetermined or untested, for suspecting a possible cause-and-effect relationship between the study drug and the occurrence of the AE, the AE should be considered “related.” The causality assessment must be documented in the source document.

The following additional guidance may be helpful:

Term	Relationship definition
Related	The temporal relationship between the event and the administration of the investigational product is compelling and/or follows a known or suspected response pattern to that product, and the event cannot be explained by the subject's medical condition, other therapies, or accident.
Not related	The event can be readily explained by other factors, such as the subject's underlying medical condition, concomitant therapy, or accident, and no plausible temporal or biologic relationship exists between the investigational product and the event.

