## 1.2 Product Background and Clinical Information

Ganaxolone is the 3 $\beta$ -methylated synthetic analogue of the neuroactive steroid allopregnanolone, but it is designed not to activate nuclear (classical) progesterone receptors. Ganaxolone differs from other GABA agents by interacting with both synaptic and extra-synaptic GABAA receptors and at binding sites distinct from benzodiazepines. Whereas benzodiazepines might lose their inhibitory action, ganaxolone does not because it selectively binds to GABAA receptors containing the  $\alpha$  and  $\delta$  subunits. By enhancing GABAA receptor function, ganaxolone provides an alternative mechanism in the treatment of seizures and could serve as effective therapy in the management of SE.

The therapeutic strategy for SE is always aggressive, and subjects in this condition often present with many comorbidities. The introduction of another medication to control SE must be balanced with the potential risks it brings, and most commonly used AEDs are associated with significant toxicities. Ganaxolone is an attractive potential therapy because of its current investigational safety profile, which is derived from a relatively large clinical database (> 1,500 subjects exposed) that contains both pediatric and adult populations. In clinical trials to date, it has shown anticonvulsant activity in subjects with seizure disorders. Marinus is investigating the approach of dosing ganaxolone to a level required to successfully control SE in this patient population.

Neuroactive steroids, which are positive allosteric modulators of both synaptic and extra-synaptic GABAA receptors, have inhibitory properties to calm the overexcited brain (some have been used as anesthetics) and might be effective in treating benzodiazepine-resistant SE.

As of 10 October 2018, approximately 1,557 unique subjects have received treatment with ganaxolone in ongoing and completed company-sponsored clinical trials ranging in duration from 1 day to more than 2 years, using doses from 50 to 2,000 mg/day.

In addition, 175 subjects were enrolled in 2 post-partum depression studies and 41 subjects have been randomized in on-going phase 3 pediatric genetic epilepsy studies.

In 20 completed Phase 1 studies, 319 healthy subjects received ganaxolone doses of 50 to 2,000 mg/day for periods of up to 2 weeks.

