The current therapies for SE have inherent risks, which must be balanced against the benefit of rapid seizure control. Benzodiazepines are the agents of choice for first line treatment of SE but their use can cause respiratory depression and hypotension, requiring the use of supportive therapies. Unfortunately, approximately 35-45% of patients are refractory to benzodiazepines. Second line therapy involves administration of an IVAED such as fosphenytoin, valproic acid, or levetiracetam for convulsive tonic-clonic status with the goal of stopping SE in patients who did not respond to first line treatment. When a patient with SE fails to respond to a benzodiazepine and the initial 2nd line therapy they are classified as having RSE. RSE develops in 31-44% of patients with SE, with a mortality of 16-39%. Additional therapeutic agents are required immediately; typically, anesthetics via continuous infusion. Currently, the recommended anesthetic drugs include midazolam, propofol, thiopental, and pentobarbital. Anesthetics are associated with risks, especially if administered for a long time – propofol infusion syndrome and hypotension are two recognized adverse events associated with anesthetics for SE treatment. In addition, the need for assisted ventilation and the management of hypotension and cardiopulmonary depression have their own risks.

Few therapies are approved for the treatment of SE and the urgent need for more efficacious therapies remains. Only two-thirds of patients in SE respond to first-line treatment. Resistance to treatment has been partially attributed to the internalization of post-synaptic GABAA-receptors and externalization of glutamate receptors. As prolonged epileptiform bursting results in a reduction of GABAA-mediated synaptic inhibition, antiepileptic treatments which rely on enhancing intra-synaptic GABAA neurotransmission become less effective the longer SE continues.

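### Protocol Section 8.1.2 gives two conflicting tests for a related adverse event, and an event with two plausible causes fits neither row of its guidance table

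*Protocol*

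**What the plan says.** Protocol Section 8.1.2 opens with a narrative rule. The investigator decides whether "there is a reasonable possibility that the event may have been caused by the study drug". If no valid reason points to a link, the AE is not related. It is related "if there is any valid reason, even if undetermined or untested, for suspecting a possible cause-and-effect relationship". Nothing in the narrative asks the investigator to exclude other causes.

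A two-row table follows, introduced with "The following additional guidance may be helpful":

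- *Related*: the timing is compelling, or the event fits a known or suspected response pattern, or both, "and the event cannot be explained by the subject's medical condition, other therapies, or accident".
- *Not related*: other factors readily explain the event, and "no plausible temporal or biologic relationship exists between the investigational product and the event".

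No text says which of the two governs if they disagree.

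The label then decides what is recorded late in the study. Under Section 8.1, items a and b, the weekly follow-up visits are restricted: only "ongoing AEs and new AEs assessed by the investigator to be related to study drug will be recorded".

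**The concern.** The table is meant to help investigators apply the narrative, but its *Related* row adds a condition that the narrative does not contain: no other explanation may be available. In this population that condition is hard to meet. Protocol Section 1.2 says that "subjects in this condition often present with many comorbidities". Inclusion criterion 4 requires concurrent second-line IV AED therapy. Section 2.1 says of benzodiazepines, the first-line treatment, that "their use can cause respiratory depression and hypotension, requiring the use of supportive therapies", and names hypotension as a risk of the anesthetics. Ganaxolone's own expected effect is sedation (Section 1.2). For sedation or hypotension, then, a drug link and a competing explanation will often coexist.

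Two investigators who see the same event could label it differently, depending on which half of Section 8.1.2 they follow. The study has one treatment and no control arm (SAP Section 1), so there is no comparator rate against which to judge attribution, and investigator causality carries more weight than it would in a controlled trial.

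**Working it through.** No arithmetic applies, because the documents give no figure on this point. The check has two parts: run every type of event through both tests, then trace where the label is used.

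**Part 1: the two tests side by side.** Classify an event by whether a drug link is plausible and whether another cause readily explains it.

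| Plausible drug link | Other ready explanation | Narrative | *Related* row | *Not related* row |
|---|---|---|---|---|
| Yes | No | Related | Met if timing is compelling or a pattern is known or suspected | Not met |
| Yes | Yes | Related | Not met (another explanation exists) | Not met (a link is plausible) |
| No | Yes | Not related | Not met | Met |
| No | No | Not related | Not met | Not met (no ready explanation) |

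The narrative puts every event in exactly one category. The table does not. The second line is the important one: an event with two plausible causes is related under the narrative and has no place in the table. The fourth line is a smaller gap of the same kind. It arises because the *Not related* row joins its two conditions with *and*.

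**Part 2: what depends on the label.**

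- SAP Section 4.9.1 and Protocol Section 9.8: summary of treatment-emergent AEs by relationship.
- Protocol Section 4.5.1, criterion 6: withdrawal for a related SAE (criterion 5, on rash, also refers to relatedness).
- Protocol Section 8.2.7: notification of related, unexpected SAEs to US authorities, active sites and central IRBs.
- Protocol Section 8.2.4: SAEs discovered after the study are reportable only if related.
- Protocol Section 8.1, items a and b, and Table 1 footnote u: recording of new AEs at the weekly contacts.

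**What does not depend on it.**

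- All AEs through the in-patient follow-up day are recorded (Section 8.1; Table 1 footnote u).
- All SAEs from first dose to last contact are recorded (same places).
- Ongoing AEs continue to be recorded at the weekly contacts.
- A named list is recorded at the weekly contacts whatever the relatedness: urinary tract infection, hospital-acquired or ventilator-associated pneumonia, myocardial infarction, sepsis, critical illness myopathy or neuropathy, and hypotension needing vasopressors. The Synopsis and Table 1 footnote u apply this list to all subjects. Section 8.1 states it only in item b, for subjects who stop without a taper.

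The only events that can go unrecorded altogether because of the label are therefore new, non-serious, unlisted AEs at Weeks 2 to 4. For everything else the event is kept and only its label is in doubt.

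**The case against.** The strongest reply is that the narrative is the operative rule. It uses directive language, it covers every case, and it already makes a dual-cause event related. The table is offered only as optional help, so an investigator who follows the narrative makes no error. This stands, and it means that harm arises only where investigators lean on the table. It does not remove the contradiction. A short table with two labelled rows is what a busy site is likely to consult, and guidance should not reverse the rule it illustrates.

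A reader might infer that the table moves dual-cause events into *Not related*. It does not. That row also requires that no plausible link exists, so strictly the table leaves these events unclassified. That they would more often be called not related is a judgement about how people choose between two boxes, not something the text directs.

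A reader might also infer that related events are broadly lost from the data. The documents do not support that either, given what is recorded regardless. The infusion lasts about 48 hours, and Section 1.2 expects plasma levels to fall rapidly afterwards, with low levels possibly persisting for several days. New drug-related sedation or hypotension in Weeks 2 to 4 is thus unlikely, and hypotension needing vasopressors is on the named list.

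Two further points reduce the weight of the concern. The withdrawal list is permissive, and criterion 4 covers any safety issue without a relatedness test. The SAP's analysis is descriptive: AEs are also tabulated irrespective of relationship and are all listed.

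**Conclusion.** The concern holds in a limited form. Section 8.1.2 contains two incompatible causality tests and does not say which prevails. The *Related* row is wrong as written when set against the narrative.

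The likely direction is too few events labelled related. This rests on two assumptions: that some investigators use the table, and that, faced with an event fitting neither row, they tend to choose not related. The first is reasonable, the second probable, and the documents prove neither.

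The size cannot be estimated. The documents do not say how many drug-suspect events have a competing cause or how sites use the table. Any assumed share would simply come back as the answer. The consequence is confined to the label, with its uses listed above, and to the narrow group of late non-serious AEs that might not be recorded. It does not touch the primary endpoint.

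**What to change.** Three changes to Section 8.1.2:

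1. Rewrite the *Related* row to match the narrative: a reasonable possibility of a causal link, even if other causes are also possible.
2. Keep *Not related* for events with no plausible temporal or biologic link, and do not make a ready alternative explanation a further requirement. The two rows then cover every event, including the fourth line of the comparison above.
3. State that the narrative governs.

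Carry the same wording into the eCRF guidelines. For events already classified, the study report should say which test the sites were told to apply. The corrected wording should also be in place before any of this text is reused in the separate phase 3 study that the SAP announces.

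The cost is protocol and guideline wording. The one downside is that the related-AE rate may rise, which should be explained where rates before and after the change are compared.
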